CHAGNING HABITS AND LIFESTYLES IN OLDER INDIVIDUALS

Registration: NCT02777918

Date of Document: 26.07.2018

INCREASING EGG AND DIETARY PROTEIN INTAKE IN COMMUNITY-DWELLING OLDER ADULTS USING RECIPES AND SINGLE-USE HERB / SPICE PACKETS: A RANDOMIZED CONTROLLED TRIAL

METHODS

The study used a parallel group, randomized controlled intervention design, where community-dwelling older adults were randomized to receive or not receive high-protein egg-based recipes and herb/spice packets for 12 weeks, and egg intake, protein intake, and measures of health and well-being were measured at baseline, at the end of 12 weeks and after a further 12 weeks.

Participants

Older adults were considered for inclusion in the study if they were: 55 years and over; living in the community; not allergic to eggs; not knowingly suffering from hypercholesterolaemia or familial hypercholesterolaemia; not knowingly suffering from known renal insufficiency; not having undergone chemotherapy or radiotherapy in the last 6 months; not suffering from any condition, or receiving treatment that affected eating or sense of flavour; were able to give consent and complete all questionnaire measures; and did not have a pacemaker or defibrillator. These inclusion criteria allowed inclusion of volunteers within our target population (older adults living in the community), while ensuring against adverse health consequences as a result of a change in eggs or dietary protein consumption (British-Heart-Foundation, 2015; Pedrini, Levey, Lau, Chalmers, & Wang, 1996) or involvement in the study, and valid outcome assessments (Jacobsen et al., 1993; Steinbach et al., 2009; Van Cutsem & Arends, 2005).

Sample size:

Data from the National Diet and Nutrition Survey (NDNS) show that UK adults over 65 years old have a mean daily protein intake of 69.8g (SD = 20.3) (Bates et al., 2014). Assuming a threshold to stimulate muscle protein synthesis of 25-30g protein per meal (Paddon-Jones & Rasmussen, 2009) for three meals per day, daily intake should be at least 75-90g per day, an increase of on average 12.7g of protein per day. Assuming no change in the control group over the intervention period, and an alpha of 5% for a power of 0.8, the required sample size to detect a 12.7g increase in protein intake in the intervention group equals 41 participants per group. Taking into account a possible drop-out of 20%, we aimed to recruit 50 participants per study group.

Recruitment:

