A schematic overview of the study design can be found in Figure 1. All participants came to Bournemouth University for a test session at baseline (T1), after 12 weeks intervention (T2), and after a further 12 weeks (T3). A week before each test session, participants received a set of questionnaires by post, to complete and bring to the test session. Queries were discussed at the test session, but on a few occasions, participants finished the questionnaires at home within a few days after the test session, and returned them by post. All test sessions were conducted in the morning between 8.00 and 11.00, at a time of the participant's preference. Participants came fasted, and were asked to have had only water to drink since going to sleep the night before the test session. Height and weight were measured first, followed by bioelectrical impedance measures of body composition. After these measures, a breakfast of toast / cereal and coffee / tea was provided. While the participant was eating breakfast, questionnaires were checked for missing values and any queries were discussed. After breakfast, the functional measures of lean muscle mass were undertaken. Questionnaires and tests undertaken were the same for each test session (T1, T2, T3), excepting that demographic and lifestyle characteristics, and reasons for eating / not eating eggs were only assessed at baseline. Test sessions were individual, or if preferred per couple, and lasted approximately an hour per person. After the baseline test session, all participants also received a postcard with a short dietary information message, including the importance of dietary protein for older adults and why it may be beneficial to eat more protein, and to do so for breakfast. This was included to add relevance to the recipes for those in the intervention group, but made no reference to the recipes or intervention, but was identical for all participants.

Blinding:

Outcome assessments were undertaken by a researcher who was blind to intervention group ([name]). Recipes and herb/spice packets were sent to intervention participants by a researcher with no direct contact with participants ([name]). Participants were not blind, although they were blind to the other possible conditions, thus the control group did not know about the intervention, nor the details of the intervention. Participants in the intervention group were asked not to mention the recipes to researchers.

Ethical Approval and Trial Registration

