Ethical approval for this study was granted by the Research Ethics Committee of Bournemouth University, prior to commencement. Participant recruitment started in May 2016, and test sessions were run from June 2016 to April 2017. The study was registered at ClinicalTrials.gov in May 2016 (NCT02777918).

Data analyses

Data were analysed using IBM SPSS Statistics for Windows, version 22, using an Intention-to-treat approach. First, all measures were tested for normality. All baseline measures were then compared

between the intervention and control group using χ^2 tests and Mann-Whitney U tests. Demographic and lifestyle characteristics were used to describe the sample. Correlations were investigated between all baseline measures. Multiple linear regression analyses were then used for the main analyses (Vickers & Altman, 2001). The effect of the intervention on all outcome measures was assessed using multiple linear regression, controlling for age, gender, baseline measures of the dependent variable, previous participation in related studies, and measures of total protein intake, BMI, usual physical activity and HR QoL score as assessed at the same time. Previous participation was included in regression models to allow for possible demand characteristics. Energy intake was not included in regression models following high correlations with BMI. Other demographic and lifestyle characteristics were also not included to maintain statistical power (Howell, 2012]. Separate regression models were used to predict egg intake, total protein intake, protein intake from animal sources, adverse events, lean body mass, physical performance, handgrip strength, and leg extensions as the dependent variables. Similar analyses were conducted once at the end of the 12 week intervention (T2) and once at the end of the following 12 weeks (T3). Egg intakes from the two different measures were compared using correlations and multiple linear regressions were conducted for both measures. Reasons for eating / not eating eggs and details on recipe feedback will be analysed further at a later date. These data and some of the data of participant demographic and lifestyle characteristics will be published elsewhere in exploratory analyses investigating intervention success / failure. Missing data were completed using last observation carried forward. Data are reported using means and standard deviations.

Figure 1: Schematic overview of the study design

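### T2 and T3 are analysed in separate regressions with no T3-minus-T2 contrast, so the change in effect after recipe deliveries end has no planned estimate, interval or test

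*Combined protocol and SAP*

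**What the plan says.** The opening of the Methods states that outcomes "were measured at baseline, at the end of 12 weeks and after a further 12 weeks". The Procedure section says that participants came "for a test session at baseline (T1), after 12 weeks intervention (T2), and after a further 12 weeks (T3". The Intervention section has recipes and herb/spice packets posted for the first twelve weeks only.

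For the analysis, Data analyses states: "The effect of the intervention on all outcome measures was assessed using multiple linear regression". Each model adjusts for age, gender, the baseline value of the outcome and previous participation, and also for "measures of total protein intake, BMI, usual physical activity and HR QoL score as assessed at the same time". On timing it says: "Similar analyses were conducted once at the end of the 12 week intervention (T2) and once at the end of the following 12 weeks". On missing values it says: "Missing data were completed using last observation carried forward".

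The document contains no repeated-measures model, no group-by-visit term and no T3-versus-T2 comparison. It also states no hypothesis about maintenance or fading.

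**The concern.** What T3 adds, beyond a second look at the group difference, is information on what happens to that difference once deliveries end. Two unconnected regressions leave that quantity unestimated. A reader will then tend to take 'significant at T2, not at T3' as the effect wearing off, and 'significant at both' as the effect being fully maintained. Neither inference follows. The difference between a significant and a non-significant result need not itself be significant, and the two estimates come from the same people, which separate models ignore.

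Two other features of the section make the pair of coefficients harder to compare:

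- **Carried-forward values.** Last observation carried forward puts the T2 value into a missing T3, sets that person's change to zero and pulls T3 towards T2.
- **Same-visit covariates.** Four adjustment variables are measured after randomisation at the visit being analysed, so the T2 and T3 coefficients are conditioned on different values.

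**Working it through.** **Inputs from the Sample size section.** The planning source gives "UK adults over 65 years old have a mean daily protein intake of 69.8g (SD = 20.3". The target is "an increase of on average 12.7g of protein per day". Alpha is 5%, power 0.8, with 41 per group.

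**Assumed.** The documents give no correlation between T2 and T3, so a range is shown. Protein intake in g/day is used throughout.

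**1. The plan's own figure.** n = 2 × 20.3² × (1.96 + 0.84)² / 12.7² = 40.1, rounded up to 41 per group. This matches the plan (two-sided; one-sided would give 32). Power at 41 is 0.81.

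**2. What the T3 regression gives alone.** On the planning SD, with no gain from covariates, SE = 20.3 × √(2/41) = 4.48 g and the 95% half-width is 1.96 × 4.48 = 8.8 g. If the full 12.7 g is still present at week 24, the T3 test has the planned power of about 0.81.

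**3. How often two verdicts mislead when nothing has changed.** Take the two test statistics as bivariate normal, each with mean 1.96 + z(power), and correlation ρ between the estimates.

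| Power at each visit | ρ | Verdicts disagree | T2 significant, T3 not |
|---|---|---|---|
| 0.8 | 0.5 | 22.6% | 11.3% |
| 0.8 | 0.7 | 17.4% | 8.7% |
| 0.8 | 0.8 | 14.2% | 7.1% |
| 0.7 | 0.5 | 28.6% | 14.3% |
| 0.7 | 0.7 | 21.9% | 10.9% |
| 0.7 | 0.8 | 17.8% | 8.9% |

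The last column is the one that would be misread as fading. The disagreement column also counts the reverse pattern.

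**4. The opposite error.** If half the effect is lost (12.7 to 6.35 g), both tests are still significant in 26-29% of trials for ρ from 0.3 to 0.9. That pattern invites a claim of full maintenance.

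**5. Precision of the direct contrast.** The SD of the within-person T3-T2 change is 20.3 × √(2(1 − ρ)), and the SE of the group difference in change is that SD × √(2/41).

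| Raw T2-T3 ρ | SE (g) | 95% half-width (g) | Power, complete fade | Power, half fade | n per group, 80% power, half fade |
|---|---|---|---|---|---|
| 0.3 | 5.30 | 10.4 | 0.67 | 0.22 | 225 |
| 0.5 | 4.48 | 8.8 | 0.81 | 0.29 | 161 |
| 0.7 | 3.47 | 6.8 | 0.95 | 0.45 | 97 |
| 0.9 | 2.01 | 3.9 | >0.99 | 0.89 | 33 |

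With baseline adjustment at an assumed baseline correlation of 0.5, the residual SD is 20.3 × √(1 − 0.25) = 17.58. Residual T2-T3 correlations of 0.5 and 0.7 then give 1.96 × 17.58 × √(2(1 − ρ)) × √(2/41) = 7.6 and 5.9 g. Those residual values imply raw correlations of 0.25 + 0.75 × 0.5 = 0.63 and 0.25 + 0.75 × 0.7 = 0.78. If all raw correlations are 0.5, the residual correlation is 0.33 and the half-width is 8.8 g. Hence the working range of about 6-9 g.

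**6. Size of the carry-forward pull.** As an assumed worst case, suppose all of the planned 20% drop-out falls between T2 and T3 and the effect fades completely. T3 would still show 0.20 × 12.7 = 2.5 g.

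**The case against.** A reader might infer that the trial cannot say whether the effect persisted, or that comparing two p-values is the only reading on offer. The documents support neither. The T3 regression is a comparison of randomised groups at week 24, adjusted for baseline, and it directly addresses whether a difference is still present 12 weeks after deliveries end. Each regression also yields a group coefficient, so effect sizes can be set side by side.

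Nor does the document set out to measure fading. It describes T3 only as a further assessment. The second 12 weeks are also not plainly free of intervention: the recipe cards were printed to last, and the Recipe feedback section has a form on recipe use sent again after that period. An error rate for a claim of fading attaches to a claim the plan never says it will make.

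The contrast is also weak. Power for half fade is 0.22-0.45 for ρ of 0.3-0.7, so a contrast close to zero would not show maintenance, and it would equally fit no effect at either visit. Finally, the document is dated July 2018, test sessions ended in April 2017 and the analysis is written in the past tense, so nothing can now be pre-specified.

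All of this stands, and it limits the point to inference about change. It does not supply the missing estimate. Setting two coefficients side by side gives no interval for their difference, and the carried-forward values and same-visit covariates make even that informal comparison unsafe.

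**Conclusion.** The point holds in limited form. The week-24 group difference is estimated, and it is the right basis for saying that an effect is still present. What is missing is any planned inference on how much the effect changed between week 12 and week 24. Paired significance verdicts cannot stand in for it: with no true change and 80% power at each visit, they would suggest fading in about 7-11% of trials (9-14% at 70% power), for assumed correlations of 0.8-0.5. This limits interpretation of the follow-up. It is not a failure of a stated aim, and the absence of a contrast does not invalidate the T2 comparison. The correlations are assumptions throughout, and the gram figures rest on the planning SD and 41 per group.

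**What to change.** For each continuous outcome, fit one likelihood-based repeated-measures model to the observed T2 and T3 values, not to values filled by carrying forward. Include group, visit, group × visit, baseline value × visit, age, gender and previous participation, with an unstructured covariance. Leave out the covariates measured after randomisation at the same visit.

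Report three quantities with 95% CIs: the group difference at T2, the group difference at T3, and the T3-minus-T2 change. Base statements that an effect is still present on the T3 difference. Base statements about the amount of fading or maintenance on the contrast and its interval, and make none from paired p-values. Adverse events are collected as reports of symptoms occurring more or less often than usual, so they need a model suited to that form.

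**Cost.** One model per outcome, on data already collected, in the software named, with no extra visits or participants. The contrast will be imprecise (about ±6-9 g/day for protein, and wider if the T2-T3 correlation is below 0.5) and has low power for partial fading. Report it as an interval, and label it a supplementary analysis because testing has ended.

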Participants were recruited via contact lists of individuals who have volunteered in previous studies; organisations that ran group meetings within the target population, e.g. bridge clubs; and by flyers and posters at local community buildings, such as museums and libraries. All volunteers were initially screened for suitability by telephone or email, and they were sent a participant information sheet before coming to the University for the baseline test session. Screening was repeated at this test session, and consent completed. Participants were not informed of the aim of the study, but were instead told the project was studying habits and lifestyles in older adults.

Randomisation:

All eligible volunteers were randomized into one of two groups: intervention and control, following consent. Randomisation was stratified per ten year age group (55-64, 65-74, 75-85, 85+) and by earlier involvement in related research [ref], using blocks of 6-10 participants, with an exception that couples were always allocated to the same group. Randomization was undertaken by a researcher with no direct contact with participants ([name]).

Intervention

Community-dwelling older adults randomized to the intervention group received six high-protein egg-based recipes and herb/spice packets every two weeks to their home address, for twelve weeks. Recipes were intended to provide ideas for consuming eggs in different ways and using different flavours, to increase variety in the overall diet. Each recipe contained one or two eggs, and provided 25-30g of protein per meal.

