Our primary outcomes were egg intake, protein intake (total), protein intake from animal-based foods and adverse events. Secondary outcomes were lean body mass and various functional measures of lean body mass. Variables of potential influence on these outcomes were also assessed, to include various demographic and lifestyle characteristics, energy intake, BMI, usual physical activity levels, health-related quality of life, reasons for eating / not eating eggs, and recipe feedback (intervention group only) Morton et al., 2017). Some of these additional variables were included in analyses to control for potential confounding, some were used only to describe the sample and some were used to investigate further any reasons for intervention success or failure.

Primary Outcomes:

Egg intake: Egg intake was measured using two measures: an egg consumption Food Frequency Questionnaire (FFQ) measure [ref] and the egg section of a validated FFQ [SCG-FFQ, Clark, 2017; Masson et al., 2003]. The egg consumption FFQ requested frequency of consumption of 18 preparations of egg: boiled eggs (hot), hard boiled eggs (cold), fried eggs, scrambled eggs, poached eggs, omelettes, scotch eggs, quiches/savoury flans, egg sandwiches, egg salad, custards, meringues, sweet flan/crème caramel, duck/quail's eggs, raw eggs, egg yolk separate from the white, and egg white separate from the yolk. For each type of egg, participants were asked to complete number of measures (e.g. 1 egg, 1 slice) consumed per day (1, 2, 3, 4, 5+) on number of days per week, using response options 1 - 7 days per week, once or twice per month, or rarely / never. Responses were converted to number of eggs eaten per month, where the category 'rarely or never' was counted as 0 times eaten per month, 'once or twice per month' as 1.5 times, and 1 to 7 days per week, as 4, 8, 12, 16, 20, 24, and 28 times per month, respectively. All foods were considered to contribute equal portions of eggs, excepting the egg dishes custards, meringues, and sweet flan / crème caramel, where each consumption was considered as 0.5 portions, because a standard portion tends to be less than one egg.

The SCG-FFQ is a validated FFQ, developed by the Scottish collaborative group, measuring dietary intake over the last two-three months (Clark, 2017; Masson et al., 2003). The section on egg intake consists of

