three questions: number of measures (eggs) per day, and the number of days per week they eat 'Boiled or poached eggs'; 'Fried eggs'; and 'Scrambled eggs or omelette'. Response options were used and converted to monthly egg intake as above.

Protein intake: Protein intake was measured using the complete SCG-FFQ, where food intake data were converted to protein intake and protein intake from animal sources, by the Scottish collaborative group (Clark, 2017). Protein intake from animal sources consisted of protein intake from meat, fish, eggs, and dairy foods. Protein intake is known to be related to egg intake (Ruxton, Derbyshire, & Gibson, 2010, questionnaire study), to muscle mass, strength and function (Houston et al., 2008; Loenneke, Loprinzi, Murphy, & Phillips, 2016; Tieland et al., 2012), and to positive health outcomes in older adults (Hannan et al., 2000; Lord, Chaput, Aubertin-Leheudre, Labonté, & Dionne, 2007). Animal based proteins contain all essential amino acids and are considered high quality protein sources (van Vliet, Burd, & van Loon, 2015). Animal protein stimulates a higher net protein synthesis than a high plant protein diet (Pannemans, Wagenmakers, Westerterp, Schaafsma, & Halliday, 1998). These measures also allowed investigation of any replacement of other high protein foods by egg based protein foods.

Adverse events: To assess adverse events, participants were asked whether during the previous month they had experienced any of the following effects more or less often than usual: nausea, digestive issues (e.g. constipation or diarrhoea), stomach aches/cramps, hunger, bloating/uncomfortable fullness, thirst, headaches, fatigue/tiredness, restlessness, dizziness, or skin rashes. If they answered yes to any of these questions, they were asked if they knew of any reason for this, or they had experienced anything else that was different than usual.

Secondary Outcomes:

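### LOCF is the only missing-data rule: a missed visit is filled with an earlier value, including pre-intervention adverse-event reports at T2, and no sensitivity analysis is described

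*Combined protocol and SAP*

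**What the plan says.** The Data analyses section gives the analysis an intention-to-treat label and then one rule for gaps: "Missing data were completed using last observation carried forward". No justification, alternative method or sensitivity analysis appears anywhere in the combined protocol and SAP.

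The same section fits separate regressions at T2 and at T3. It adjusts for the baseline value of the outcome and for "measures of total protein intake, BMI, usual physical activity and HR QoL score as assessed at the same time". As worded, LOCF fills these covariates as well as the outcomes.

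The Outcomes section states: "Our primary outcomes were egg intake, protein intake (total), protein intake from animal-based foods and adverse events". For the last of these, "participants were asked whether during the previous month they had experienced any of the following effects more or less often than usual". Under Procedure, the questionnaires are the same at T1, T2 and T3 apart from demographics and lifestyle and the reasons for eating or not eating eggs, so the adverse-event item was also asked at T1. Procedure adds that questionnaires were looked over for gaps at the session, and that a few were finished at home and posted back.

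On expected loss, the Sample size section says: "Taking into account a possible drop-out of 20%, we aimed to recruit 50 participants per study group". This is a planning allowance. No observed loss is given.

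**The concern.** With only three visits, LOCF has two specific consequences. A participant who misses T2 is analysed at T2 with a value recorded before any recipe arrived. A participant who misses only T3 is analysed at T3 with the value from the end of the intervention. T3 comes 12 weeks after the recipes stopped, so the second substitution builds in the persistence that the visit is there to examine.

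For adverse events the mismatch is one of content. A T1 report describes the month before baseline, so when carried to T2 it cannot contain a symptom that began during the intervention.

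All four primary outcomes are filled by this rule. If visits were missed, the T2 and T3 estimates can be off in either direction, depending on when and from which arm people left. With no second analysis described, a reader has nothing to judge that by.

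**Working it through.** **Inputs.** From Sample size: effect 12.7 g, SD 20.3 g, 50 per group, 20% allowance for loss. From Procedure: visits at T1, T2 and T3. Assumed, because the documents do not give them: the timing and split of loss, correlation between visits of 0.4 to 0.8, any shared drift, and adverse-event rates.

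**The plan's own figure.** The increase is (75 + 90)/2 − 69.8 = 12.7 g. The size per group is 2 × [20.3 × (1.960 + 0.842)/12.7]² = 40.1, rounded up to 41, as stated (two-sided 5%, power 0.8). The sample size is not at issue; it supplies the effect and SD used below.

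**Equal random loss, no drift.** Let q1 be the fraction of each arm lost before T2, q2 the fraction lost between T2 and T3, and D2 and D3 the true effects. Randomisation makes the expected difference at T1 zero, so carried baseline values contribute nothing:

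- T2 under LOCF = (1 − q1) × D2
- T3 under LOCF = (1 − q1 − q2) × D3 + q2 × D2

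With D2 = 12.7 g:

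| Lost before / after T2 | T2 (g) | T3 if D3 = 0 (g) | T3 if D3 = 6.35 (g) | T3 type I error, D3 = 0 |
|---|---|---|---|---|
| 5% / 5% | 0.95 × 12.7 = 12.1 | 0.05 × 12.7 = +0.6 | 0.90 × 6.35 + 0.635 = 6.35 | about 5-6% |
| 10% / 10% | 0.90 × 12.7 = 11.4 | 0.10 × 12.7 = +1.3 | 0.80 × 6.35 + 1.27 = 6.35 | about 6-8% |
| 20% / 0 | 0.80 × 12.7 = 10.2 | 0 | 0.80 × 6.35 = 5.1 | no bias |
| 0 / 20% | 12.7 | 0.20 × 12.7 = +2.5 | 0.80 × 6.35 + 2.54 = 7.6 | 10-17% |

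The error rates come from simulation (50 per arm, SD 20.3 g, regression on group and baseline, 3,000 to 6,000 replicates). The ranges span the assumed correlations.

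**Unequal loss with a shared drift s.** T2 under LOCF = (1 − qI)(D2 + s) − (1 − qC)s, where qI and qC are the fractions lost before T2 from the intervention and control arms. With 30% v 10% lost, no effect and s = +5 g, this is 0.7 × 5 − 0.9 × 5 = −1.0 g, with simulated type I error about 5-8%. With s = −5 g it is +1.0 g. Some shared change is plausible because every participant was sent a message about protein after baseline. Its size is an assumption.

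**Carried-forward covariates.** Adding three same-time covariates (assumed correlation 0.3 with protein, unaffected by group, also carried forward) moves the gram figures by about 0.1 g at most. In that larger model the 10% / 10% error rate is about 6-9%. Neither model covers outcomes adjusted for same-time total protein.

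**Adverse events.** Suppose 10% report at baseline and in controls, 30% truly report on intervention at T2, and 20% of each arm is lost at random. LOCF gives (0.8 × 0.30 + 0.2 × 0.10) − 0.10 = 16 points against a true 20. If instead 10% of the intervention arm leave with a new symptom, the truth is 30% v 10%, LOCF gives 20% v 10%, and observed reports alone give 20/90 = 22% v 10%.

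**Replacement.** A joint likelihood analysis of T1, T2 and T3 in the equal random-loss scenarios has T3 bias of at most 0.16 g and type I error of 4.1-5.2%.

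**The case against.** The trial is powered on change over the intervention, so T2 matters most, and there the practical cost is modest. With all 20% lost before T2, LOCF power at correlations of 0.4, 0.6 and 0.8 is 0.81, 0.91 and 0.99, against 0.85, 0.93 and 0.995 for observed data only. The error is also conservative under equal random loss without drift. This stands.

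The 10-17% error rate needs all 20% to leave after T2 and the effect to have vanished. This also stands; at 5% + 5% the rate is close to nominal.

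If drop-outs went back to usual eating, carrying baseline forward may be about right at T2. With 20% lost before T2 the truth would then be 10.2 g, LOCF would give 10.2 g, and a missing-at-random model would give 12.7 g. This is a strong argument for sensitivity analyses. It does not defend LOCF as the only analysis, and it does not help at T3, where the carried value comes from the end of the intervention.

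The check of questionnaires at sessions limits missing items, but it cannot supply a visit that did not take place. The intention-to-treat label keeps people in their arm but does not say what their outcome was.

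A reader might infer that LOCF inflated the trial's effect, that 20% of participants were lost, or that baseline adverse-event reports did enter T2. The documents support none of these. They give no observed missingness, and this is a methods text, so the absence of attrition counts is not itself a fault of the plan.

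**Conclusion.** The point holds in conditional form. The plan states one rule that, for anyone who missed a visit, puts a pre-intervention value into T2 or an end-of-intervention value into T3, and it offers no check on the result. Under equal random loss without drift, T2 is diluted (12.1 to 10.2 g instead of 12.7 g for 5% to 20% lost before T2). T3 can be too small or too large: it overstates a vanished effect by 0.6 to 2.5 g when 5% to 20% are lost after T2. False-positive rates run from near nominal to 10-17% in the extreme case. Upward bias at T2 needs unequal loss with a shared change, or loss related to outcome.

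These sizes are illustrations for total protein in a group-plus-baseline model, not estimates of what happened. They do not extend to egg intake, animal protein or adverse events as adjusted in the plan. The adverse-event mismatch follows from the one-month recall at any rate of loss; the rate decides only how many records are affected. The point merits a change, but it does not show that the trial's conclusions are wrong.

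**What to change.** For the continuous outcomes, replace LOCF with one of two methods:

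- a likelihood-based repeated-measures model with T1, T2 and T3 as joint outcomes and a group-by-visit term; or
- multiple imputation by group, which also imputes any same-time covariates kept in the model.

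Keep LOCF as a sensitivity analysis. Add one in which drop-outs return to baseline or control-like values, because the main method assumes data missing at random and would overstate T2 if drop-outs resumed usual intake.

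Do not carry adverse-event reports forward. Report observed events beside withdrawals by arm and visit, and say that observed reports may still undercount. As the example shows, the gain here is more in openness than in accuracy.

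Label the re-analysis post hoc, since "test sessions were run from June 2016 to April 2017". Otherwise stay as close as possible to the planned adjustment, so that a changed result can be attributed to the missing-data method. The clustering of couples and the choice of same-time covariates are separate issues and not part of this change.

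The cost is a text revision and some re-analysis of data already collected, plus reliance on a missing-at-random assumption that the sensitivity analyses are there to probe. No new data are needed.
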